1.1 Synopsis

Protocol Title: Phase 2a Study Evaluating the Efficacy, Safety, Tolerability and Pharmacokinetics of Tarlatamab in Chinese Subjects with Advanced Small Cell Lung Cancer after Two or More Prior Lines of Treatment (DeLLphi-307)

Short Protocol Title: Phase 2a Study Evaluating Tarlatamab in Chinese Subjects with Advanced Small Cell Lung Cancer after Two or More Prior Lines of Treatment (DeLLphi-307)

Study Phase: 2a

Indication: Small Cell Lung Cancer (SCLC)

Study Rationale

Small cell lung cancer (SCLC) is a grave diagnosis, marked by high initial response rates to platinum-based first-line chemotherapy. However, resistance to subsequent treatments quickly emerges, resulting in a median survival of 10 to 12 months post-diagnosis (Rudin et al, 2015). Delta-like ligand 3 (DLL3) is typically intracellular in normal tissues but often overexpressed on the cell surface in most SCLC tumors, making it an attractive target for T-cell therapies (Saunders et al, 2015). Notably, minimal cytoplasmic staining is observed in the brain, pituitary, and pancreatic islets in normal tissues (Study 123377), suggesting the potential for tumor-specific DLL3-targeted therapy.

Tarlatamab (INN; AMG 757) is a novel, extended half-life (HLE) bispecific T-cell engager (BiTE®) designed to direct T effector cells toward DLL3-expressing cells using a tandem single-chain fragment crystallizable (scFc) for prolonged half-life. In an ongoing phase 2 study (Study 20200491), tarlatamab has demonstrated efficacy in SCLC patients with a manageable safety profile (Ahn et al, 2023).

Tarlatamab received accelerated approval from the United States Food and Drug Administration (FDA) for the treatment of adult patients with extensive-stage SCLC with disease progression on or after platinum-based chemotherapy.

Study 20230273 aims to assess tarlatamab's efficacy, safety, tolerability, and pharmacokinetics (PK) in Chinese subjects with advanced SCLC who have progressed on or recurred following 1 platinum-based regimen as first-line (1L) therapy (including a Programmed Cell Death Protein 1 [PD-1]/Programmed Cell Death Ligand 1 [PD-(L)1]) and at least 1 other prior line of therapy (re-treatment with a platinum-based regimen is

considered a second-line of therapy). Detailed information about tarlatamab's chemistry, pharmacology, efficacy, and safety is available in the investigator's brochure.

Objective(s) and Endpoint(s)/Estimand(s)

Objectives	Endpoints
Primary	

 Evaluate efficacy of tarlatamab as assessed by objective response rate (ORR) based on blinded independent central review (BICR) per Response Evaluation Criteria in Solid Tumors version 1.1 (RECIST 1.1) 	
 ORR BICR, defined as proportion with best overall response (BOR) of complete response (CR) plus partial response (PR)
Secondary	

 Evaluate efficacy of Tarlatamab as assessed by duration of response (DOR), disease control (DC), and progression-free survival (PFS) based on BICR per RECIST 1.1 	
 DOR, defined as time from the first documentation of objective response (OR) until the first documentation of disease progression or death due to any cause, whichever occurs first. Only subjects who have achieved OR will be evaluated for DOR DC, defined as CR + PR + stable disease (SD) Duration of DC, defined as time from the first documentation of CR, PR, or SD until the first documentation of disease progression or death due to any cause, whichever occurs first. Only subjects who have achieved CR, PR, or SD will be evaluated for Duration of DC PFS, defined as time from enrollment until disease progression or death from any cause, whichever occurs first. Progression will be based on RECIST 1.1.

 Evaluate efficacy of Tarlatamab as assessed by ORR, DOR, DC, and PFS based on investigator assessment per RECIST 1.1 	
 ORR (Investigator) DOR DC Duration of DC PFS

 Evaluate efficacy of Tarlatamab as assessed by overall survival (OS) 	
 OS, defined as time from enrollment until death from any cause

• Evaluate safety and tolerability	
• Incidence of treatment-emergent adverse events

• Characterize the pharmacokinetics of tarlatamab	
• Serum concentration of tarlatamab

• Evaluate the immunogenicity of tarlatamab	
• Incidence of anti-tarlatamab antibody formation

Estimand(s) for Primary Objective(s)

Objective response rate (ORR) by blinded independent central review (BICR) per RECIST 1.1 in Chinese subjects with advanced SCLC who have progressed on or recurred following 1 platinum-based regimen as 1L therapy (including a PD-1/ PD [L]1) and at least 1 other prior line of therapy (re treatment with a platinum-based regimen is considered a second line of therapy) prior to start of new cancer therapy (while-on-treatment strategy).

Overall Design

This is a phase 2a, multicenter, single arm, open-label study in Chinese subjects with advanced SCLC who have progressed on or recurred following 1 platinum-based regimen as 1L therapy (including a PD-1/PD-[L]1) and at least 1 other prior line of therapy (re-treatment with a platinum-based regimen is considered a second-line of therapy).

The study consists of a 21-day screening period, a treatment period, a safety follow-up (SFU) period, and a long-term follow-up (LTFU) period. Enrolled subjects will receive tarlatamab per protocol.

Number of Subjects

Approximately 30 Chinese subjects are planned to be enrolled in the study.

Summary of Subject Eligibility Criteria

Male and female subjects who are residents in China and of Chinese ancestry, aged ≥ 18 years (or legal adult age), with confirmed advanced SCLC after 1 platinum-based regimen as 1L therapy (including PD-1/PD-[L]1) and at least one other prior line of therapy.

Upon study consent, subjects undergo protocol-mandated screening assessments to confirm eligibility. They must have measurable lesions (per RECIST 1.1) within 21 days before the first dose of study treatment and adequate organ function.

For a full list of eligibility criteria, please refer to Section 5.1 to Section 5.2.

Treatments

Tarlatamab will be administered as a 60-minute (\pm 10 minutes) intravenous (IV) infusion with 1 mg step dose on cycle 1 day 1 (C1D1) followed by a 10 mg target dose on cycle 1 day 8 (C1D8), and cycle 1 day 15 (C1D15) in a 28-day cycle. Subsequent doses (10 mg) will be administered every 2 weeks (Q2W) (ie, cycle 2+ day 1/day 15 dosing) in a 28-day cycle.

- Monitoring during cycle 1:
 - Monitoring – cycle 1: Monitoring required for 6 to 8 hours post-infusion at C1D1 and C1D8.
 - Cohabitant (caregiver) support for 24 hours post-infusion and the ability to stay within 1 hour of a hospital for 24 hours is required.
 - Counseling the subject and caregiver on signs and symptoms of cytokine release syndrome (CRS), and immune effector cell-associated neurotoxicity syndrome (ICANS) by a health care provider is required prior to discharge.
 - Subjects return to site on cycle 1 day 2 (C1D2) and cycle 1 day 9 (C1D9) for vital signs and physical examination.
 - At subsequent visits, additional monitoring may be required post-infusion. Refer to Section 6.1.1 (Table 6-1).
- Pre- and Post-infusion medication requirements:
 - Dexamethasone: 8 mg IV (or equivalent) will be administered within 1 hour prior to tarlatamab infusion on C1D1 and C1D8.
 - Intravenous Hydration: 1 L normal saline over 2 to 4 hours following tarlatamab administration on C1D1 and C1D8.

Statistical Considerations

For a full description of statistical analysis methods, please refer to [Section 9](#).

[figure not shown]
Statistical Hypotheses

No statistical hypotheses will be tested.

Sponsor Name: Amgen Inc.

1.2 Study Schema

Figure 1-1. Study Schema

C1D1 = cycle 1 day 1; C1D8 = cycle 1 day 8; C1D15 = cycle 1 day 15; IV = intravenous; Q2W = every 2 weeks; RECIST 1.1 = Response Evaluation Criteria in Solid Tumors 1.1

^a Subjects will receive study treatment until blinded independent central review (BICR)-**confirmed** disease progression per RECIST 1.1, death, withdrawal of consent, start of new anticancer therapy, unacceptable toxicity, or end of study as determined by the sponsor (whichever occurs first).

^b End of Treatment visit will occur at the time the decision is made to discontinue study treatment (preferably within 14 days after last dose of study treatment) and prior to start of new anti-cancer therapy.

^c Safety Follow-up visit will occur **60** (+ 5) days after last dose of study treatment.

1.3 Schedule of Activities (SoA)

Table 1-1. Schedule of Activities: Cycle 1 only

Procedure ^a	Screening	Treatment Period ^b					As clinically indicated	Notes
		Cycle 1						
Day	(Up to 21 Days Before Day 1)	1	2	8	9	15		
GENERAL AND SAFETY ASSESSMENTS								
Informed consent	X							
Inclusion and exclusion criteria	X							
Medical history	X							Includes medical, surgical, and cancer.
Demographics	X							
Physical examination (including neurological exam)	(X)	[X]	X	X	X	X	X	Physical exam must be completed prior to start of infusion on treatment days. (X): Height to be collected at screening ONLY. [X]: Must include weight on Day 1.
Vital Signs	X	(X)	X	(X)	X	X	X	Includes systolic/diastolic blood pressure, heart rate, respiratory rate, pulse oximetry, and temperature. (X): Refer to Section 8.4.1 for detailed vital sign collection time points.
ECOG PS	X	X						

Footnotes defined on last page of this table.

Table 1-1. Schedule of Activities: Cycle 1 only

Procedure ^a	Screening	Treatment Period ^b					As clinically indicated	Notes
		Cycle 1						
Day	(Up to 21 Days Before Day 1)	1	2	8	9	15		
NYHA	X							Collected at screening only for patients with a known history of heart disease.
ECG	X						X	
ECHO or MUGA scan	X						X	
Adverse events		continuous					X	
Serious adverse events	continuous						X	
Prior and Concomitant therapies review	continuous						X	
LABORATORY ASSESSMENTS								
HIV, Hepatitis B and C screening	X						X	
Pregnancy test (females of childbearing potential only) ^c	X	X					X	Serum pregnancy test at screening within 7 days of C1D1; serum or urine pregnancy test on Day 1 of every cycle should be collected.
Coagulation ^d	X	X		X		X	X	
Hematology ^d	X	X		X		X	X	
Chemistry ^d	X	(X)		X		X	X	(X): Includes LDH and uric acid.

Footnotes defined on last page of this table.

Table 1-1. Schedule of Activities: Cycle 1 only

Procedure ^a	Screening	Treatment Period ^b					As clinically indicated	Notes
		Cycle 1						
Day	(Up to 21 Days Before Day 1)	1	2	8	9	15		
Urinalysis ^d	X	X					X	
Lipase and amylase ^e	X	X					X	
TSH and FT4 ^e	X	X					X	
CENTRAL LABORATORY ASSESSMENTS								
PK sample		X						X: Collect pre dose sample on C1D1. The time of dosing and PK sample collection should be accurately recorded.
Anti-tarlatamab antibody sample		X						X: Collect pre dose sample on C1D1. Refer to Section 8.7 for additional details.
IMAGING ASSESSMENTS								
MRI brain	X ^f						X	All brain scans on protocol are required to be MRI unless MRI is contraindicated, then CT with contrast is acceptable. Subsequently after screening, MRI brain can be performed at any time if clinically indicated per standard of care.

Footnotes defined on last page of this table.

Table 1-1. Schedule of Activities: Cycle 1 only

Procedure ^a	Screening	Treatment Period ^b					As clinically indicated	Notes
		Cycle 1						
Day	(Up to 21 Days Before Day 1)	1	2	8	9	15		
Radiological imaging and tumor assessment ^g	X ^f	Weeks 1 to 48: Q6W (± 1 week) Weeks 49+ Q12W (± 1 week) by BICR per RECIST 1.1					X	Refer to Section 8.3.1 for additional details. For subjects who end study treatment for reasons other than specified in Section 8.3.2, every effort should be made to perform scheduled radiographic imaging (CT/MRI) until radiographic progression.
STUDY TREATMENT AND MONITORING								
Other protocol-required therapy: Dexamethasone		X		X				Refer to Section 6.1.2 for details for pre-treatment with dexamethasone (or equivalent dose of other corticosteroids). Dexamethasone will be administered within 1 hour prior to tarlatamab infusion on days 1 and 8 of cycle 1 only.
Tarlatamab Infusion		X		X		X		

Footnotes defined on last page of this table.

Table 1-1. Schedule of Activities: Cycle 1 only

Procedure ^a	Screening	Treatment Period ^b					As clinically indicated	Notes
		Cycle 1						
Day	(Up to 21 Days Before Day 1)	1	2	8	9	15		
Monitoring post-tarlatamab infusion		X		X			X	Subject will remain at study site for 6 to 8 hours post-infusion at C1D1 and C1D8 Cohabitant (caregiver) support for 24 hours post-infusion and the ability to stay within 1 hour of a hospital for 24 hours is required. Counseling the subject and caregiver on signs and symptoms of CRS and ICANS by a health care provider is required prior to discharge. Subjects return to site on C1D2 and C1D9 for vital signs and physical examination. At subsequent visits, additional monitoring may be recommended post-tarlatamab infusion based on occurrence of CRS, ICANS, or ICANS-related neurological events. Refer to Table 6-1 .
Other protocol-required therapy: IV hydration		X		X				Refer to Section 6.1.2 for details related to IV hydration. IV hydration (1 L normal saline) over 2 to 4 hours following tarlatamab administration.

Page 5 of 5

BICR = Blinded Independent Central Review; C1D1 = cycle 1 day 1; C1D2 = cycle 1 day 2; C1D8 = cycle 1 day 8; C1D9 = cycle 1 day 9;

CRS = cytokine release syndrome; CT = computed tomography; ECG = electrocardiogram; ECHO = echocardiogram; ECOG PS = Eastern Cooperative Oncology Group Performance Status; EOI = end of infusion; FT4 = free T4; HIV = human immunodeficiency virus; ICANS = immune effector cell-associated neurotoxicity syndrome; IV = intravenous; LDH = Lactate dehydrogenase; MUGA Scan = multigated acquisition scan; MRI = magnetic resonance imaging; NYHA = New York Heart Association; PK = pharmacokinetic; Q6W = every 6 weeks; Q12W = every 12 weeks; RECIST 1.1 = Response Evaluation Criteria in Solid Tumors 1.1; TSH = thyroid-stimulating hormone

^a All procedures and assessments on dosing days are to be completed prior to study drug administration unless otherwise indicated. Assessments should not be performed from the infusion line.

^b Each visit week and day is relative to day 1 of each cycle. Cycle 1 visits have a \pm 1-day window from designated time point unless otherwise specified.

- ^c Additional on-treatment pregnancy testing may be performed at the investigator's discretion if there is suspicion that a female subject is pregnant or per local laws and regulations.
- ^d **If screening local labs are obtained within 48 hours prior to cycle 1 day 1 dose, pre-infusion cycle 1 day 1 samples do not have to be repeated. Where applicable, cycle 1 day 8 and day 15 local labs must be obtained within 48 hours prior to dose (day 8 and day 15). Results must be reviewed prior to study drug administration.**
- ^e **If screening local labs are obtained within 72 hours prior to cycle 1 day 1 dose, the pre-infusion cycle 1 day 1 samples do not have to be repeated. Results must be reviewed prior to study drug administration.**
- ^f Imaging assessments must be within 21 days prior to the first dose of tarlatamab.
- ^g Timing is based on first dose of tarlatamab (C1D1).

Table 1-2. Schedule of Activities: Cycle 2+

Procedure ^a	Treatment Period ^b				EOT ^c	SFU ^d	LTFU ^{e,f}	As clinically indicated	Notes
	Cycle 2		Cycle 3+						
Day	1	15	1	15					
GENERAL AND SAFETY ASSESSMENTS									
Physical examination (including neurological exam)	[X]	X	[X]	X	X	X		X	Physical exam must be completed prior to start of infusion on treatment days. [X]: Must include weight on Day 1 of every cycle.
Vital Signs	X	X	X	X	X	X		X	Includes systolic/diastolic blood pressure, heart rate, respiratory rate, pulse oximetry, and temperature
ECOG PS	X		X		X	X			
ECG					X			X	
Adverse events	continuous							X	
Serious adverse events	continuous ^g							X	
Prior and Concomitant therapies review	continuous							X	
Survival Status							X		
Subsequent anticancer therapy					X	X	X		
LABORATORY ASSESSMENTS									
Pregnancy test (females of childbearing potential only) ^h	X		X		X	X	(X)	X	Serum or urine pregnancy test on Day 1 of every cycle should be collected. (X): 60 days after the last dose of tarlatamab.

Footnotes defined on last page of this table.

Table 1-2. Schedule of Activities: Cycle 2+

Procedure ^a	Treatment Period ^b				EOT ^c	SFU ^d	LTFU ^{e,f}	As clinically indicated	Notes
	Cycle 2		Cycle 3+						
Day	1	15	1	15					
Coagulation ⁱ	X	X	X		X	X		X	
Hematology ⁱ	X	X	X	(X)	X	X		X	(X): Cycle 3, 4, and 5 only.
Chemistry ⁱ	[X]	X	X	(X)	X	X		X	[X]: Includes LDH and uric acid on C2D1 only. (X): Cycle 3, 4, and 5 only.
Urinalysis	X		(X)		X	X		X	(X): Collect on cycle 3, cycle 4 and then every other cycle (ie, cycle 6, 8, etc) on Day 1 only.
Lipase and amylase ^j	X		X		X	X		X	
TSH and FT4 ^j					X			X	
CENTRAL LABORATORY ASSESSMENTS									
PK sample ^k	X		(X)						All PK samples are collected pre-dose (ie, prior to start of tarlatamab infusion). (X): Collect C3D1, C4D1, and then every other cycle (ie, cycle 6, cycle 8, etc) on Day 1 only. PK samples to be collected up to cycle 12 only. The time of dosing and PK sample collection should be accurately recorded.
Anti-tarlatamab antibody sample	X		(X)		X	X			All anti-tarlatamab antibody samples are collected pre-dose (ie, prior to start of tarlatamab infusion). The time of dosing and anti-tarlatamab antibody sample collection should be accurately recorded. (X): Collect C3D1, C4D1, and then every other cycle (ie, cycle 6, cycle 8, etc) on Day 1 only. Anti-tarlatamab antibody samples are to be collected until EOT and SFU.

Table 1-2. Schedule of Activities: Cycle 2+

Procedure ^a	Treatment Period ^b				EOT ^c	SFU ^d	LTFU ^{e,f}	As clinically indicated	Notes
	Cycle 2		Cycle 3+						
Day	1	15	1	15					
IMAGING ASSESSMENTS									
Radiological imaging and tumor assessment ^k	Weeks 1 to 48: Q6W (± 1 week) Weeks 49+ Q12W (± 1 week) by BICR per RECIST 1.1				(X)	(X)	[X]	X	Refer to Section 8.3.1 for additional details. (X): For subjects who discontinued treatment for any reason other than radiographic PD, imaging is required at the EOT or SFU visit if the subject has not had radiologic imaging performed within 6 weeks of the visit (if ending treatment on or before week 48) or within 12 weeks of the visit (if ending treatment after week 48). [X]: For subjects who discontinued treatment for any reason other than specified in Section 8.3.2 , every effort should be made to perform scheduled radiographic imaging (CT/MRI) until radiographic progression.
STUDY TREATMENT AND MONITORING									
Tarlatamab Infusion ^l	X	X	X	X					
Monitoring post-tarlatamab infusion								X	At subsequent visits, additional monitoring may be recommended post-tarlatamab infusion based on occurrence of CRS, ICANS, or ICANS-related neurological events. Refer to Table 6-1 .

Footnotes defined on last page of this table.

BICR = Blinded Independent Central Review; C1D1 = cycle 1 day 1; C2D1 = cycle 2 day 1; CRS = cytokine release syndrome; ECHO = echocardiogram; ECG = electrocardiogram; ECOG PS = Eastern Cooperative Oncology Group Performance Status; EOI = end of infusion; EOT = end of treatment; FT4 = free T4; HIV = human immunodeficiency virus; ICANS = immune effector cell-associated neurotoxicity syndrome; LDH = Lactate dehydrogenase; LTFU = long-term follow-up; MUGA scan = multigated acquisition scan; PD = progressive disease; PK = pharmacokinetic; Q6W = every 6 weeks; Q12W = every 12 weeks; RECIST 1.1 = Response Evaluation Criteria in Solid Tumors Version 1.1; SFU = safety follow-up; TSH = thyroid-stimulating hormone.

- ^a All procedures and assessments on dosing days are to be completed prior to study drug administration unless otherwise indicated. Assessments should not be performed from the infusion line.
- ^b Cycle 2 and all subsequent visits have a \pm 3-day window, unless otherwise specified.
- ^c Subjects who permanently discontinue treatment for any reason are encouraged to complete all remaining study visits and procedures through LTFU to ensure safety surveillance and/or collection of outcome data. Upon permanent discontinuation from tarlatamab treatment for any reasons, an EOT visit will be performed as soon as possible (within 14 days) after last dose of tarlatamab and prior to start of subsequent anticancer therapy.
- ^d Safety follow-up visit will occur **60** (+ 5) days after the last dose of tarlatamab. Safety follow-up visits will occur regardless of initiation of subsequent anticancer therapy within that period.
- ^e Assessed every 12 weeks (\pm 14 days) up to 1 year after the last subject's last dose of tarlatamab or 5 years from first subject enrolled, whichever occurs first. The study duration for subjects will be approximately up to 24 months, however this duration will be extended as needed to ensure all subjects have the opportunity to be followed in LTFU for at least 1 year after the last subject's last dose of tarlatamab.
- ^f During LTFU, any serious adverse events suspected to be related to investigational product that the investigator becomes aware of will be reported to Amgen immediately and no later than 24 hours of awareness.
- ^g After end of study, serious adverse events suspected to be related to investigational product will be reported to Amgen. Please refer to Section 8.4.6.4 for additional details.
- ^h Additional on-treatment pregnancy testing may be performed at the investigator's discretion if there is suspicion that a female subject is pregnant or per local laws and regulations
- ⁱ Local **labs** must be obtained within 48 hours prior to dose on dosing days for tarlatamab. Laboratory results must be reviewed prior to study drug administration.
- ^j Labs must be obtained within 72 hours prior **to dose on dosing days for tarlatamab** and must be reviewed by the investigator before each dose. If labs are to be obtained more than 72 hours before the dose, prior approval by the medical monitor is required.
- ^k Timing is based on first dose of tarlatamab (C1D1).
- ^l For information on tarlatamab treatment beyond progression, refer to Section 6.1.7. Subjects who continue on treatment should follow assessments as shown in the Schedule of Activities.

2. Introduction

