8.4.3 Clinical Laboratory Assessments

Refer to Section 11.2 for the list of clinical laboratory tests to be performed and to the Schedule of Activities (Section 1.3) for the timing and frequency.

The investigator is responsible for reviewing laboratory test results and recording any clinically relevant changes occurring during the study in the Events CRF. The investigator must determine whether an abnormal value in an individual study subject represents a clinically significant change from the subject's baseline values. In general, abnormal laboratory findings without clinical significance (based on the investigator's judgment) are not to be recorded as adverse events. However, laboratory value changes that require treatment or adjustment in current therapy are considered adverse events. Where applicable, clinical sequelae (not the laboratory abnormality) are to be recorded as the adverse event.

All protocol-required laboratory assessments, as defined in Section 11.2, must be conducted in accordance with the laboratory manual and the Schedule of Activities (Section 1.3).

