11.2 Appendix 2. Clinical Laboratory Tests

The tests detailed in [Table 11-1](#) will be performed by the central laboratory and/or by the local laboratory. Additional analyte test results may be reported by the local or central laboratory, in accordance with standard laboratory procedures (eg, components of a hematology panel).

Protocol-specific requirements for inclusion or exclusion of subjects are detailed in [Sections 5.1](#) to [5.2](#) of the protocol.

Additional tests may be performed at any time during the study as determined necessary by the investigator or required by local regulations.

Table 11-1. Analyte Listing

Local Laboratory: Chemistry	Local Laboratory: Coagulation	Local Laboratory: Urinalysis	Local Laboratory: Hematology	Other Lab Analytes
Sodium Potassium Chloride Bicarbonate or CO ₂ Total protein Albumin Calcium Magnesium Phosphorus Glucose BUN or serum urea Creatinine Creatine Kinase Uric acid Total bilirubin Direct bilirubin ALP LDH AST (SGOT) ALT (SGPT)	PT/INR PTT/APTT	Blood Protein Glucose Bilirubin	RBC Hemoglobin MCV Platelets WBC Differentials: 5-part differential: • Lymphocytes • Monocytes • Eosinophils • Basophils • Total Neutrophils or (Segmented Neutrophils and bands/stabs 3-part differential if unable to perform 5-part: • Lymphocytes • Granulocytes • Monocytes OR • Lymphocytes • Neutrophils • Mid-cell fraction	Central Laboratory: Anti-tarlatamab antibodies Tarlatamab PK Local Laboratory: Serum or Urine Pregnancy HIV Antibody testing Hepatitis serology testing (DNA/RNA by PCR as needed) Hep B surface antigen Hep B core antibody Hep C virus antibody Amylase Lipase TSH FT4

ALP = alkaline phosphatase; ALT = alanine aminotransferase; AST = aspartate aminotransferase;
 APTT = activated partial thromboplastin time; BUN = blood urea nitrogen; CO₂ = carbon dioxide; DNA =
 deoxyribonucleic acid; FT4 = free T4 Hep = hepatitis; HIV = human immunodeficiency virus;
 INR = international normalized ratio; LDH = lactate dehydrogenase; MCV = mean corpuscular volume; PCR
 = polymerase chain reaction; PK = pharmacokinetics; PT = prothrombin time; PTT = partial thromboplastin
 time; RBC = red blood cell count; RNA = ribonucleic acid; SGOT = serum glutamic-oxaloacetic
 transaminase; SGPT = serum glutamic-pyruvic transaminase; TSH = thyroid-stimulating hormone;
 WBC = white blood cell count

If the subject is being followed for possible drug-induced liver injury (DILI), the following

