11.11.3 Tumor Lysis Syndrome

Common Terminology Criteria for Adverse Events (CTCAE) version 5.0 classifies TLS in grade 3 (present), grade 4 (life threatening consequences; urgent intervention indicated) and grade 5 (death). Cairo and Bishop developed a system for defining and grading TLS based on Hande-Garrow classification of laboratory or clinical TLS (Coiffier et al, 2008). In this trial, the Cairo-Bishop classification will be used to define presence of TLS; ie, presence of laboratory TLS (see [Table 11-8](#)) and clinical TLS. Final event grade will be assigned according to CTCAE version 5.0.

Based on the Cairo and Bishop system, laboratory TLS is defined as any 2 or more abnormal serum values present within 3 days before or 7 days after initiation of treatment in the setting of adequate hydration (with or without alkalinization) and use of a hypouricemic agent ([Table 11-8](#)).

Table 11-8. Cairo-Bishop Definition of Laboratory Tumor Lysis Syndrome

Element	Value	Change from baseline
Uric acid	$\geq 476 \mu\text{mol/L}$ or 8 mg/dL	25% increase
Potassium	$\geq 6.0 \text{ mmol/L}$ or 6 mg/L	25% increase
Phosphorus	$\geq 2.1 \text{ mmol/L}$ for children or $\geq 1.45 \text{ mol/L}$ for adults	25% increase
Calcium	$\leq 1.75 \text{ mmol/L}$	25% decrease

Note: Two or more laboratory changes within 3 days before or 7 days after cytotoxic therapy will constitute laboratory tumor lysis syndrome.

Clinical TLS requires the presence of laboratory TLS in addition to 1 or more of the following significant complications: renal insufficiency, cardiac arrhythmias/sudden death, and seizures.

Approval Signatures

Document Name: Protocol Amendment tarlatamab 20230273 2

Document Description: Tarlatamab 20230273 PA1- development for a China only study

Document Number: CLIN-000332994

Approval Date: 06 Sep 2024

Type of Study Protocol: Amendment

Protocol Amendment No.: 2

Document Approvals	
Reason for Signing: Management	Name: [REDACTED] Date of Signature: 06-Sep-2024 15:25:09 GMT+0000

Amendment 1

Protocol Title: Phase 2a Study Evaluating the Efficacy, Safety, Tolerability, and Pharmacokinetics of Tarlatamab in Chinese Subjects with Advanced Small Cell Lung Cancer after Two or More Prior Lines of Treatment (DeLLphi-307)

Amgen Protocol Number: 20230273

Amendment Date: 15 May 2024

Rationale:

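### On the better-supported reading of the Schedule, uric acid is not drawn between C1D1 and C2D1, so no scheduled value covers the 7 days after first dose used to define laboratory TLS (minor)

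*Protocol*

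**What the plan says.** **Schedule (Protocol 1.3).** The chemistry row of Table 1-1 shows a plain X at screening, a bracketed X on Day 1, a plain X on Days 8 and 15, and an as-clinically-indicated entry. Days 2 and 9 are blank. The note for the bracketed mark is "X): Includes LDH and uric acid". Table 1-2 uses the same device for later cycles: "X]: Includes LDH and uric acid on C2D1 only". Footnote d to Table 1-1 says that "cycle 1 day 8 and day 15 local labs must be obtained within 48 hours prior to dose" and that results are reviewed before dosing. It also says that, when screening labs fall within 48 hours of the first dose, "pre-infusion cycle 1 day 1 samples do not have to be repeated".

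**Panel (Protocol 8.4.3 and 11.2).** Section 8.4.3 takes the tests from Section 11.2 and their visits from the Schedule; its wording is "for the list of clinical laboratory tests to be performed and to the Schedule of Activities (Section 1.3) for the timing and frequency". Table 11-1 has 20 analytes in its chemistry column. Uric acid ("Creatine Kinase Uric acid Total bilirubin") and LDH are among them, with no visit restriction.

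**Use of the result (Protocol 11.11.3, Table 6-2, 2.3).** Laboratory TLS means two or more abnormal values among uric acid, potassium, phosphorus and calcium, "within 3 days before or 7 days after initiation of treatment". Clinical TLS requires laboratory TLS first. Table 6-2 has dosing interrupted or delayed at once when TLS is present. Section 2.3 classes TLS as a potential safety issue and includes it in a strategy of monitoring and early recognition.

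**The concern.** The definition that triggers a dosing decision looks back over the 7 days after first dose. If the Schedule is followed as marked, one of its four elements has no scheduled value in that stretch. The C1D8 results are reviewed just before the step from 1 mg to 10 mg, which is when a laboratory signal after the first dose would be most useful. Because clinical TLS depends on laboratory TLS, an unrecognised laboratory pattern could also keep a clinical event from meeting the protocol's definition. Separately, two sites could read Section 1.3 and Table 11-1 differently and collect different panels. The stake is patient safety and consistent ascertainment of TLS, not efficacy.

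**Working it through.** The plan gives no figure to reproduce. The check is visit-window arithmetic plus a comparison of the two sections.

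**Inputs.**
- First dose is day 1 (Protocol 8.1.2), taken here as offset 0.
- Cycle 1 visits have a ±1 day window (Table 1-1, footnote b); visits from cycle 2 have ±3 days (Table 1-2, footnote b).
- Labs may be drawn up to 48 hours, or 2 days, before the dose (Table 1-1, footnote d; Table 1-2, footnote i).
- Procedures on dosing days come before the infusion (footnote a), so the C1D1 draw is pre-dose.

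**Formula.** Earliest draw = (nominal day − 1) − visit window − 2. Latest draw = (nominal day − 1) + visit window.

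| Draw | Earliest | Latest | Within 7 days of first dose? | Marked for uric acid? |
|---|---|---|---|---|
| C1D1 | pre-dose | pre-dose | in the 3-days-before part | yes |
| C1D8 | 7 − 1 − 2 = +4 | 7 + 1 = +8 | yes, except at +8 | no |
| C1D15 | 14 − 1 − 2 = +11 | 14 + 1 = +15 | no | no |
| C2D1 | 28 − 3 − 2 = +23 | 28 + 3 = +31 | no | yes |

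For C1D8, the three visit days (+6, +7, +8) crossed with draws 0, 1 or 2 days earlier give 9 whole-day combinations. Eight are at or before +7; the exception is a visit one day late with a same-day draw. C1D8 is therefore the only scheduled chemistry draw that can fall in the 7 days after first dose. The C2D1 range assumes no dose delay; by then the subject has had three infusions (1, 10 and 10 mg).

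**C1D15 relative to the first 10 mg dose.** Earliest: +11 − 8 = 3 days after. Latest: +15 − 6 = 9 days after.

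**Which reading of the Schedule?** If every chemistry draw were the full Table 11-1 panel, the Day 1 note would add nothing and the restriction to C2D1 in Table 1-2 would be false. Section 8.4.3 also leaves timing to the Schedule. Both points favour reading a plain X as chemistry without uric acid and LDH. On that reading the number of required uric acid values in the 7 days after first dose is 0; on the full-panel reading it is 1.

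**What a site following the mark would miss.** Potassium, phosphorus and calcium are still drawn at C1D8, so any two of them establish laboratory TLS. Uric acid changes the answer only when exactly one of those three is abnormal. Even then, the definition does not require the values to come from one draw, and the C1D1 uric acid lies inside the window. A value already abnormal at C1D1 could be paired with one abnormal element at C1D8. What remains unseen is a uric acid rise that is new after first dose, together with exactly one of the other three.

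**The case against.** **The gap may not exist.** Table 11-1 has no visit limits, and Section 8.4.3 requires the assessments defined in Section 11.2 to be done. The protocol also repeats itself elsewhere, for example on pregnancy testing, so a redundant note is not decisive. This stands in part: the omission is the better-supported reading, not a certainty. It does not explain away the C2D1 restriction in Table 1-2, and an ambiguity that sites can resolve differently is itself worth removing.

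**Safeguards remain.** Three of the four elements are drawn and reviewed at C1D8. Chemistry can be drawn whenever clinically indicated, Section 11.2 allows additional tests at any time, subjects are examined on C1D2 and C1D9, and hydration is mandatory after the first two infusions. All of this stands and keeps the point minor.

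**It is the sponsor's choice.** TLS is only a potential risk, and the documents give no incidence or timing that would show the present sampling to be inadequate. That is fair, and it is why the change is offered as a cheap improvement rather than the correction of an error.

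**A stronger inference.** Three of the six possible two-element pairs include uric acid, so a reader might infer that half of qualifying TLS would go undetected. The documents do not support this. Pairs are not equally likely, a count of pairs is not a case rate, patterns with three or four abnormal elements are still caught, and the C1D1 value can supply the uric acid element.

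**Conclusion.** The point holds as a minor design improvement. On the better-supported reading, uric acid is required before the first dose and then not until +23 to +31 days, while the TLS window closes at +7. At a site following the mark, scheduled labs would miss only cases that rest on a post-dose uric acid rise plus exactly one of potassium, phosphorus or calcium. How many that is cannot be sized: the documents give no TLS rate, and the SAP derives no laboratory TLS variable. No efficacy result is affected.

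The conclusion assumes that a plain X means chemistry without uric acid, that draws follow the stated windows, and that the TLS window runs from the first dose, as Section 11.11.3 words it.

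A reader might also infer that footnote d lets a site skip uric acid at C1D1 by substituting a screening panel that lacks it. The text does not go that far. Read analyte by analyte, only what has already been measured need not be repeated, so uric acid would still be due.

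**What to change.** 1. In Table 1-1, mark the C1D8 chemistry cell so that uric acid is drawn and reviewed before the first 10 mg dose.
2. Preferably mark C1D15 as well. It lies outside the window counted from first dose, but it is the next scheduled chemistry draw after the first 10 mg dose, which the C1D8 draw precedes.
3. In Table 11-1, state that the Schedule sets the visits for uric acid and LDH. If the sponsor in fact intends the full panel at every chemistry draw, deleting the marks in both tables would settle the matter equally well.
4. Optionally, add to footnote d that a screening panel replaces the C1D1 panel only for analytes it contains.

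The cost is one extra local analyte on blood already drawn at each newly marked visit, plus the wording. Reusing the existing bracketed mark unchanged would also bring in LDH; a separate mark avoids that. The gain is modest: one uric acid value 4 to 8 days after the 1 mg step dose and, if C1D15 is marked, one 3 to 9 days after the first 10 mg dose.
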